2.1 Primary endpoint

The primary outcome of the study is the absolute number and point estimate (with 95% CIs) of the proportion of participants with TB microbiological confirmation starting TB treatment within 7 days of their first visit. We evaluate the probability of the patients in the intervention arm (with Truenat) for a favourable outcome of interest compared to patients in the SOC arm as a binary outcome of success or failure.

The hypotheses of interest are:

and,

 ${\it H0}:$ Number of successes in intervention arm is same as in the SOC arm.

H1: Number of successes in intervention arm is different from the SOC arm

H0: Proportion of success in intervention arm is same as in the SOC arm.

H1: Proportion of success in intervention arm is different from the SOC arm

This is translated in terms of odds ratio (OR) for odds of success in the intervention arm to be different from the odds of success in the SOC arm thus leading to the definition of the following hypothesis:

QMS Form number: FM-06-02-	CONFIDENTIAL	Page 6 of 26
05/v2.0		-

FIND >>>	Statistical Analysis Plan		
Protocol number:	TB041-3/1-TAN / -MOZ		
Document version:	5.0	Document date:	11-JUL-2023

 $H0: OR_{Intervention:SOC} = 1 \text{ vs. } H1: OR_{Intervention:SOC} \neq 1$

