4.1 General approach

All analyses will be performed on the MITT and PP populations. Because there was a protocol deviation (i.e. participants with missing V2 or V3), the potential difference in the primary outcome between the two populations will be explored as described in *Section 7.0*.

All analyses (i.e. generalized linear models and proportional hazards models) will take into account the effect of the clusters using a mixed model approach, introducing a random intercept for each cluster. Details of the models for each outcome are given in the sections below.

For all statistical tests, alpha will be set to 0.05 for rejecting the null hypothesis. Since multiple comparisons will be performed, p-values will be adjusted using Benjamini-Hochberg method.

The proportion of observations with missing values will be summarised for all outcome variables. Missing and invalid data will not be imputed. Baseline measures will be reported for individuals with missing data on an outcome of interest, including those who withdraw or are lost to follow-up. For each analysis, the baseline measures (demographic and laboratory data) will be compared between participants with complete and incomplete data using T-Tests or Chi² tests, for continuous or categorical variables respectively.

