4.3 Analysis of the secondary outcomes

Diagnosis, treatment, and morbidity related endpoints

The analysis of the binary outcomes will be performed in the same way as the analysis of primary outcomes using GLMMs with Poisson or binomial distributions, for count or proportion data respectively.

Time-to-event analyses will be performed using mixed-effect Cox proportional hazards (PH) regression models (*coxme* package, *coxme* function in R). Kaplan Meier curves will be used to graphically represent the data. The possibility of non-proportional hazards will be assessed using Schoenfeld individual test and its graphical representation.

In case of non-proportional hazards, we will consider to split the time, use an interaction term, use a complementary log-log generalized linear model, or a combination of these approaches. If non-proportional hazard is caused by a confounder, we may set that variable as a strata.

As for primary outcome, the models will be adjusted for gender, age, HIV status, country, and asset index that is described below. In case of necessity, the models may be adjusted for the setting (i.e. urban, rural, peri-rural nesting the clusters), and site.

Direct cost and productivity, modelled cost, and cost effectiveness related endpoints:

MSeveral of these endpoints are not estimated using standard statistical analyses, but rather reflect descriptive analyses or model-based analyses that are not purely statistical in nature.

Patients' costs related to care

Patient costs will be estimated as the mean cost per patient interviewed. These costs will include direct and indirect costs incurred because of TB diagnosis. Direct costs will include all medical (including consultation fees and any out-of- pocket payment for medicines, X-rays, and diagnostics) and non-medical expenses (including travel costs of participants and caregivers,

QMS Form number: FM-06-02-	CONFIDENTIAL	Page 15 of 26
05/v2.0		_

FIND >>>	Statistical Analysis Plan		
Protocol number:	TB041-3/1-TAN / -MOZ		
Document version:	5.0	Document date:	11-JUL-2023

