Benefit incidence analysis (BIA) will be applied to assess the distribution of benefits of novel Molbio Truenat MTB/RIF platform (Int 1) compared to the hub-and-spoke standard of care (Int 0) and the centralized approach (Int 2). To conduct the analysis, data on health service utilization and unit costs for each strategy, categorized by socio-economic groups, will be estimated. Health service utilization rate will be estimated from the trial and expressed as the number and proportion of TB detected and started on treatment across each strategy and stratified by quintile (i.e., which indicates the extent to which the investments made in each diagnostic are allocated equitably, not considering only point of diagnosis, but also returning for test results, treatment initiation and any other needed follow up). The cost incurred by the public sector providers will be derived from the data gathered on unit cost of each diagnostic strategy. Regarding the SES status, a simplified asset indices adopted from standardized Equity Tool (https://www.equitytool.org/) is used to collect data on asset ownership (i.e., presence of a refrigerator, a mobile phone, a television, electricity, type of toilet, water supply, cooking fuel, and materials of the wall and floor) of study participants and a standardized scoring of these questions will be used to assign a wealth quintile for each respondents. Then health service utilization rate will then be multiplied by the unit costs of each diagnostic Intervention. The benefits of each diagnostic strategy utilization will be aggregated and expressed in monetary terms. Concentration curves and indexes will be computed to illustrate the extent of inequality in the distribution of health spending across quintile.

Extended cost-effectiveness analysis

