4.4 Analysis of missing data patterns

Additional exploratory analyses will be performed to investigate any pattern in missing data. If the outcomes will be missing at random or missing completely at random the above longitudinal data models or clustered data models considering the mixed effect regression under maximum likelihood estimation will be appropriate. Missing at random can be tested by regression the binary outcome of missing or not, with independent variables as the other covariates in the model. If this binary outcome of missingness is associated with the outcome of interest in the model framework, we expect to have the Missing Not at Random in our outcome data. In case it is dependent on other covariates but not the outcome of interest, we are likely to have Missing at Random. In the event of patterns for missing data being not random, the results of the regression will be reported and a detailed plan will be developed to assess the association between the missingness and each covariate. Depending on the results of the analyses, sources of bias will be determined and documented.

5 Baseline descriptive statistics

Descriptive statistics tables will be generated to summarize the characteristics of the participants in the PP, PPM, MITT and ITT populations. The number of participants included and excluded will be reported, overall and for each arm within the hierarchy of each cluster and site.

Among the included participants, outcomes of interest as described above as well as covariates such as sex, age (continuous and categorical as age groups defined as: 18-30, 31-40, 41-50, >50), HIV status, site (i.e. 4 different institutions), country setting (Urban, Rural, Peri-rural), RIF resistance, asset index and the variables that are used for determining the asset index will be summarized.

The summary of measurements and descriptive statistics will also be presented for the overall PP population and at the cluster level (i.e. clinic-based characteristics) for clinics in each of the study arms. The outcomes of interest are, number of patients (size of the unit), number of individuals tested positive, and number of individuals who started treatment, number of patients with presumptive TB seen, number of patients by enrolment period, number of staff at the clinic, time to TB diagnosis, time to TB treatment.

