Results will be reported in both absolute numbers (e.g. number of subjects in a group) and the proportion, or summarized by mean, median, standard deviation, minimum, maximum and quartiles. Differences in the groups of Intervention and SOC will be tested by Chi² Test or Fisher exact test for categorical outcomes, and Kruskal-Wallis test, t- test, ANOVA or Wilcoxon signed rank test for continuous data depending on whether parametric or non-parametric tests are appropriate for the observed data.

QMS Form number: FM-06-02-	CONFIDENTIAL	Page 18 of 26
05/v2.0		-

FIND >>>	Statistical Analysis Plan				
Protocol number:	TB041-3/1-TAN / -MOZ				
Document version:	5.0	Document date:	11-JUL-2023		

6 Additional sub-group analyses

All primary and secondary endpoints will be evaluated separately by sex and gender (if the information is available), HIV status, site, country, asset index, and age categories (as given in Section 5).

7 Exploratory analyses

Protocol Deviation

A proportion of participants were contacted outside of their contact window. 808 participants were affected concerning the V2, and 40 participants were affected concerning the V3. For participants where V2 was not done, V3 was also not done.

Since the data was collected retrospectively, a bias might have occurred since the participants may not recall exactly their status of treatment during the actual Day 7 and Day 60. To overcome this bias.

- 1) A list with IDs of all affected participants was formed by the data manager (15/03/2023 data extract) and reported to national IRB ref: 173/CNBS/23, and this is defined as the MPP population,
- 2) The data that was entered retrospectively was crosschecked with the TB, treatment registry at the clinic (~50 registries) to make sure the treatment initiation data was not misrecorded.
- 3) Descriptive statistics will be performed to describe the number and the percentage of the effected participants (V2, V3, and both) in both arms in the PPM population,
- 4) Descriptive statistics will be performed to describe the number and the percentage of the effected participants for the treatment outcome at day 7. Chi² test will be performed to assess the statistical significance of the difference between the PP and PPM populations. In case of statistical significance, all the models in the study will be adjusted for the deviation (TRUE/FALSE).

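### SAP section 6 evaluates every endpoint separately within subgroups and has no arm-by-subgroup test, so differences in significance between levels can be misread as effect modification

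*SAP*

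**What the plan says.** The subgroup plan is the single sentence of SAP section 6: "All primary and secondary endpoints will be evaluated separately by sex and gender (if the information is available), HIV status, site, country, asset index", followed by age category. SAP section 5 supplies some of the levels: "age groups defined as: 18-30, 31-40, 41-50, >50" for age and "site (i.e. 4 different institutions" for site. Section 6 gives no categories for the asset index. Quintiles appear only in the benefit incidence analysis in SAP 4.3, where the scoring is used to "assign a wealth quintile for each respondents".

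The models in SAP 4.2 and 4.3 include gender, age, HIV status, country and asset index as adjustment covariates, and site only if needed. The one interaction term in either document is a remedy for a different problem: "In case of non-proportional hazards, we will consider to split the time, use an interaction term". Protocol 13.5 and 13.6 plan no subgroup analysis.

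On error control, SAP 4.1 says "For all statistical tests, alpha will be set to 0.05 for rejecting the null hypothesis" and "Since multiple comparisons will be performed, p-values will be adjusted using Benjamini-Hochberg method". It does not define the family of tests or say whether subgroup tests belong to it. SAP 4.2 specifies Wald confidence intervals. SAP section 6 does not call the subgroup results exploratory; that label heads section 7, which deals with the protocol deviation.

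**The concern.** A subgroup analysis asks whether the effect differs between levels. Separate evaluation answers another question: whether the effect within each level differs from none. Each level has fewer patients or fewer clinics than the trial as a whole. Even when the effect is the same everywhere, some levels will therefore reach significance and others will not.

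Protocol section 7 says the findings are meant to guide policy on use and scale-up. A table in which the intervention appears to work in one HIV stratum, age band or wealth group and not in another invites a conclusion that the analysis cannot support. The primary result is not affected.

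**Working it through.** **1. Reproducing the plan's figure.** The inputs are the final scenario in SAP section 8 (Protocol 13.8): prevalence 12%; sensitivity 89% and 70%; diagnostic loss 2% and 10%; pre-treatment loss 10% and 20%; cluster size 150; CV 0.25; alpha 0.05; power 80%. The alternative is two-sided ("H1: Proportion of success in intervention arm is different from the SOC arm").

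- Intervention: 0.12 × 0.89 × 0.98 × 0.90 = 0.0942
- Control: 0.12 × 0.70 × 0.90 × 0.80 = 0.0605
- Variance term: 0.0942 × 0.9058/150 + 0.0605 × 0.9395/150 + 0.25² × (0.0942² + 0.0605²) = 0.000569 + 0.000379 + 0.000783 = 0.001731
- Pairs: A + 7.849 × 0.001731/0.0337² = A + 11.95

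With A = 1 (Protocol) this is 12.95, rounded up to the stated 13 pairs. One pair is then added, giving 14. The SAP text states A = 2, but its table follows A = 1, which is used here.

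**2. Power within a level when the effect is the same in all levels.** With 14 pairs, SE = √(0.001731/13) = 0.01154 and power = Φ(0.0337/0.01154 − 1.96) = 83% overall. For a factor that varies within clinics, the cluster size is replaced by 150 times the level's share:

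| Level | Share (assumed) | Power |
|---|---|---|
| Sex, each half | 50% | 65% |
| HIV, smaller / larger group | 30% / 70% | 49% / 75% |
| Age, each band | 25% | 44% |
| Asset index, each quintile | 20% | 37% |

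**3. Chance of discordant significance with no effect modification.** If levels were independent, the chance that some but not all are significant would be 1 − Πp − Π(1 − p). For sex this is 1 − 0.65² − 0.35², about 45%. Levels of these factors share clinics, however, so their results are correlated and the formula overstates the figure. The trial was therefore simulated with 14 clinics per arm, clinic proportions varying with CV 0.25 and common to all levels in a clinic, and the same true effect in every level. Each level was tested on clinic proportions with a t test. Results hold to within about a point:

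| Factor | Some but not all levels at p<0.05 |
|---|---|
| Sex | 38% |
| HIV | 44% |
| Age | 78% |
| Asset index | 83% |

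With Benjamini-Hochberg applied within each factor, the range across the four factors is about 29-55%.

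**4. Site.** 28 clinics / 4 sites = 7 per site (equal split assumed), so 4 vs 3 by arm. A cluster-level comparison then has 4 + 3 − 2 = 5 degrees of freedom, and the chance that |t| exceeds 1.96 under no effect is 10.7%. Simulation with 150 patients per clinic, proportion 0.08 and CV 0.25 gave 10.8% with the z critical value and 5.1% with the t critical value. A random-intercept logistic model also gave about 10%.

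**5. Power of the proposed interaction test.** For two equal halves treated as independent, the standard error of the difference in effects is twice that of the main effect. With 80% power for the main effect, the power for an interaction of the same size is Φ((1.96 + 0.84)/2 − 1.96) = 29%.

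**The case against.** The strongest reply is that SAP 4.1 already provides multiplicity control. This carries weight against one tempting inference. A reader might count about 19 levels over the six factors and conclude that at least one spurious significant subgroup per endpoint is more likely than not. The documents do not support that. The count treats p-values as unadjusted when the SAP adjusts them. It treats as independent levels that re-cut the same patients. It also measures any false positive under no effect at all, not disagreement between levels. The adjustment still does not answer the present point: its family is undefined, and in any family it corrects p-values within levels without comparing one level with another.

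A second reply is that the SAP says evaluated separately, not fitted in separate models, and makes no subgroup claim. That is fair. A reader might infer that the sponsor will report effect modification from these results, but the SAP is silent on interpretation. What can be said is that the plan leaves this reading open.

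Third, the few-clinic problem is a matter of small-sample inference, distinct from the missing interaction test. It should not be extended to sex, HIV status, age or asset index, for which every clinic contributes to every level.

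Last, interaction tests here will be weak. True, but low power argues for labelling the results exploratory, not for comparing p-values across levels.

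**Conclusion.** The point stands as a weakness in the subgroup analyses. With an identical effect in every level, discordant significance arises in about 38% of trials for sex, 44% for HIV status, 78% for age and 83% for asset index, or about 29-55% if Benjamini-Hochberg is applied within a factor. For site alone, Wald intervals on about 7 clinics give a type I error near 10%.

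These sizes rest on the SAP's design effect and CV and on assumptions the documents do not settle: a 50/50 sex split, binary HIV status at 30/70, equal age quarters, asset quintiles, and clinics divided equally among sites. Protocol section 11 gives unequal recruitment targets for the two Mozambique sites, so the 4 vs 3 layout is illustrative and a site with fewer clinics would fare worse. The discordance figures come from a cluster-level comparison of proportions, not from the adjusted mixed model the SAP plans. The exact percentages could shift; the absence of any comparison between levels does not depend on them.

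**What to change.** Amend SAP section 6 so that, for each subgroup factor, one mixed model is fitted to the full dataset with an arm-by-factor term. Report the interaction estimate with its 95% CI and p-value, and take the level-specific estimates from the same model. Define the asset index categories, label the results exploratory, and say whether these tests belong to the Benjamini-Hochberg family. For site, use t-based or cluster-level inference. With all 28 clinics in one analysis, a cluster-level comparison of arms by site has 28 − 8 = 20 degrees of freedom, against 5 in a single-site analysis.

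The cost is SAP wording only: no new data, and six interaction tests per endpoint in place of about 19 separate level tests. The downside is low power, about 29% for an interaction as large as the main effect in equal halves. The SAP should state this, so that a non-significant interaction is not taken as evidence of a uniform effect. For factors that vary within clinics, shared clinic effects partly cancel and power may be somewhat higher.
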